8.1.5 Protocol dose specifics

One ml given as a one-time dose.

8.1.6 Preparation

On the day of injection, the HB1.F3.CD_CRAAd-S-pk7 cell product will be prepared as described in a separate **SOP (Appendix B)**. Briefly, HB1.F3.CD_CRAAd-S-pk7 cells are removed from the vapor phase of liquid nitrogen storage and thawed in a 37° water bath. Cells are then washed with perfusion fluid central nervous system (PFCNS)+2% human serum albumin (HSA) buffer a total of three times, and resuspended in PFCNS+2% HSA and maintained at room temperature in the biosafety cabinet for up to six hours.

8.1.7 Route of administration for this study

Intratumoral at the time of surgical biopsy or resection of the tumor. Refer to Section 4.4 for product administration.

8.1.8 Incompatibilities

NA

8.1.9 Availability & Supply

Human NSCs (HB1.F3) were provided by [name]. The HB1.F3 human NSC line was established by retroviral transduction of *v-myc* into primary human NSCs isolated from fetal telencephalon of 15 weeks gestation and provided by [name], PhD. The HB1.F3 line is well-characterized and multipotent, non-tumorigenic and non-immunogenic. A phase I study was recently completed at COH which involved injection of up to 50 million NSCs which confirmed that the risk to benefit ratio merited continued study.

The cell product was manufactured at the University of Alabama and is stored in the Mathews Center for Cell Therapy at Northwestern University. The clinical grade CRAAd-S-pk7 vector has been produced in compliance with current Good Manufacturing Practices for gene therapy vectors. This is a replication competent adenoviral vector based on an adenovirus serotype-5 backbone.

8.1.10 Side effects

Toxicities Associated with Adenoviral Injection

In previous trials of intratumoral adenoviral injection, toxicity was rare, and overall, the approach has been well tolerated. A summary of grade 3 and 4 toxicities seen in the previous trials is provided in **Table 8** below. In the Phase I study in recurrent brain

tumors, CNS toxicity (lethargy, confusion, grade 3 hyponatremia, fever, leukocytosis, intratumoral hemorrhage in 1, hydrocephalus in the other) was observed in 2/2 patients at 2×10^{12} vp dose level. In the lower dose levels, no DLTs were observed but transient and less severe events included seizure, small intratumoral hemorrhage, worsening of neurologic symptoms, mild hyponatremia. One patient at the highest dose level in the prostate dose escalation study experienced grade 4 transient thrombocytopenia which was considered a DLT and also transient grade 3 elevation in liver transaminases.

Table 8 – Summary of Grade 3 and 4 Toxicities In Trials With Adenovirus		
Patient Characteristics	Treatment Specifics	Toxicity
Recurrent malignant gliomas IND 6371 13 patients Trask et al, 2000	Dose escalation: 2×10^9 vp, (2 pts) 2×10^{10} vp, (2 pts) 2×10^{11} vp, (7 pts) 2×10^{12} vp, (2 pts) Delivery: Stereotactic injection Prodrug: GCV Concurrent tx: none	CNS toxicity in 2/2 patients at 2×10^{12} vp dose level Therapy tolerated by other 11 patients including 7/7 patients treated at 2×10^{11} vp
Recurrent ovarian cancer, stage IIIC IND 7311 10 patients Hasenburg et al, 2001	Dose escalation: 2×10^{10} vp, (2 pts) 2×10^{11} vp, (2 pts) 2×10^{12} vp, (2 pts) 2×10^{13} vp, (4 pts) Delivery: Intraperitoneal Prodrug: ACV or Valacyclovir Concurrent tx: Topotecan	No significant toxicity attributable to gene therapy.
Recurrent prostate cancer IND 6636 18 patients Herman et al, 1999	Dose escalation: 2×10^9 vp, (4 pts) 2×10^{10} vp, (5 pts) 2×10^{11} vp, (4 pts) 2×10^{12} vp, (5 pts) Delivery: Intraprostatic Prodrug: GCV Concurrent tx: none	One patient at 2×10^{12} vp dose level had transient grade 4 thrombocytopenia and grade 3 hepatotoxicity
Recurrent prostate cancer (radiation failures), multiple injections 27 patients (18 new patients plus 9 additional injections in patients from first study) Shalev et al, 2000; Miles et al, 2001	Dose: $2-6 \times 10^{11}$ vp Delivery: Intraprostatic Prodrug: GCV Concurrent tx: none	Grade 3 hypertension in one patient requiring anti-hypertensive therapy
Pre-prostatectomy 41 patients in 3 studies (1 in Mexico- 10pts; 1 in Netherlands-8pts; 1 in the US-23 pts)	Rojas-Martinez; 10 pts 1×10^{11} vp Van der Linden; 8 pts 2×10^{10} vp (4pts) 2×10^{11} vp (4pts) Ayala et al, 2006: 23 pts $2-8 \times 10^{11}$ vp	No significant toxicity attributable to study drug.
Prostate cancer, combined with radiation therapy IND 8437 71 patients The et al, 2001 (1 st 30 patients)	Dose: 5×10^{11} vp per injection Delivery: Intraprostatic Prodrug: valacyclovir Concurrent tx: radiation +/- hormone	
 Grade 3 ALT elevation in 1 patient, resolving after 1 week, no interruption in therapy Grade 3 genitourinary toxicity in 1 patient attributed to the radiation therapy

Potential Biohazard Exposure to Health-Care Personnel

Personnel Involved in Vector Injection: There is a low potential for biohazard exposure to the personnel involved in vector injection. The viral vector is suspended in a small volume (~1.0 ml) of buffer and is contained in a cryovial. The syringe is loaded from the vial with no vector loss. Intratumoral injection is made and the amount of leakage along

the needle track is likely to be very minute. In the event of accidental spills of the vector from the vial common disinfectants can be used to inactivate the agent. All personnel are instructed on the safe use and potential biological hazards of the vector before the procedures are performed.

Post-Surgical Health Care Workers: There is a potential that the virus may escape the patient via urine, feces, saliva, mucus, tears or other excretions. Studies in non-human primates indicate that the potential is low. In studies with six baboons only one plaque was detected in the serum of one baboon injected two days previously with the vector (see IND application 6371 or RAC Protocol 1294-098). In semipermissive cotton rats, only minimal virus was detected after intracardiac injection (Rojas-Martinez et al, 1998). Exposure to shedded replication-competent virus will pose a very limited hazard, as the titers will be extremely low. There is a theoretical possibility that the vector could recombine with wild-type adenovirus although this has not been detected in previous patients treated with the similar adenoviral vectors. If this did occur, infection would be expected to cause a mild, self-limited infection similar to a common adenovirus infection. Health care workers will be instructed on the safe use and potential biological hazards of the virus vector before they are allowed to work with the patients.

8.1.11 Nursing implications

Nurses will not be involved handling or administration of the cell product. After administration, universal precautions should be used during hospitalization. Nurses through their usual care will participate in physical and neurological assessments that may help identify any adverse events.

8.1.12 Return and Retention of Study Drug

Unused prepared study cell product will be disposed of in a Biohazard Waste container, which will be closed and disposed of according to Biohazard Waste disposal policy. Expired unprepared or unused product in the Mathews Center for Cell Therapy will be disposed of according to BSL-2 practices.

8.2 Agent Temozolomide (started after completion of study cell product administration as a standard of care therapy)

8.1.1 Other names

Temodar

8.1.2 Classification - type of agent

Anti-neoplastic

8.1.3 Mode of action

Alkylating agent.

8.1.4 Storage and stability

Temozolomide will be stored in the patient's home at room temperature. The patient will be instructed to keep the drug out of reach of children. Drug stability is determined by the manufacturer and consistent with the drug expiration date printed on the container supplied to the patient.

8.1.5 Protocol dose specifics

Temozolomide is dosed at 75 mg/m² daily for up to 49 days, concomitant with focal radiotherapy. After a break of 4 weeks, temozolomide maintenance therapy is given for up to 6 cycles. Initial dose is 150 mg/m² with an increase to 200 mg/m² if tolerated, given as a single daily dose for 5 days every 28 days. Timing of daily administration will be per routine use and as directed by the treating

oncologist. Temozolomide dose may be delayed or modified by the treating oncologist based on patient tolerance.

8.1.6 Preparation

Temozolomide is supplied in 5, 20, 100, 140, 180 and 250 mg capsules. Daily dose is determined based on BSA calculations, with the appropriate combination of capsules to reach the closest equivalent mg/m² dose.

8.1.7 Route of administration for this study

Oral

8.1.8 Incompatibilities

Valproic acid: decreases clearance of oral temozolomide.

8.1.9 Availability & Supply

Commercially available.

8.1.10 Side effects

- The most common adverse reactions ($\geq 10\%$ incidence) are: alopecia, fatigue, nausea, vomiting, headache, constipation, anorexia, convulsions, rash, hemiparesis, diarrhea, asthenia, fever, dizziness, coordination abnormal, viral infection, amnesia, and insomnia.
- The most common Grade 3 to 4 hematologic laboratory abnormalities ($\geq 10\%$ incidence) that have developed during treatment with temozolomide are: lymphopenia, thrombocytopenia, neutropenia, and leukopenia. Allergic reactions have also been reported.
- Less likely but severe adverse reactions include myelodysplastic syndrome and hepatotoxicity

8.1.11 Nursing implications

Antiemetic prophylaxis with a 5-HT3 antagonist is recommended prior to administration of the first few temozolomide doses and should be administered orally 30 to 60 minutes before temozolomide treatment. Prophylaxis is at the discretion of the treating oncologist. Monitor complete blood count and liver function tests to determine tolerance.

8.1.12 Return and Retention of Study Drug

Patients are instructed to return any unused temozolomide to the dispensing pharmacy for appropriate disposal.

9.0 CORRELATIVES/SPECIAL STUDIES

An exploratory objective will be to evaluate serum cytokine profile and blood immune response to NSC-CRAd-S-pk7 and to determine whether overall survival rate correlates with extent of immune response. In addition, replication competent retrovirus (RCR) testing will be performed by analyzing patient DNA from whole blood for RCR-specific sequences at baseline, 3 months, 6 months, and 1 year after study treatment; and annually thereafter, and to determine whether overall survival rate correlates with persistent gene expression. Real time PCR with 4070A envelope-specific primers will be used to screen DNA extracted from PBMCs from study patients treated with NSCs.

Correlative study (sample type)	Cytokine profile (serum)	Immune response (whole blood)	RCR testing
Mandatory or Optional	Mandatory	Mandatory	Mandatory
Timing (+/- windows)	Baseline, Days 1, 3, 7, 14 and 28 after	Baseline, Days 1, 7, 14 and 28 after study	Baseline, 3 months, 6 months, and 1 year

	study product injection	product injection	after study product injection
Volume Needed (blood only)	4-5 ml	4-5 ml	4-5 ml
Tube type needed (blood only)	EDTA tube	Non-EDTA tube	Non-EDTA tube
Tissue thickness and/or # slides (tissue only)	NA	NA	NA
Processing center	Lurie Research Center (LRC) 3-250	Lurie Research Center (LRC) 3-250	Lurie Research Center (LRC) 3-250
Sample handling/processing instructions	Blood transported directly to LRC within 30 minutes of draw; centrifuge 15 minutes at 3000 rpm; pipette serum into vial and freeze at -80°C until analysis	Blood transported directly to LRC within 30 minutes of draw; freeze at -80°C until analysis	Blood transported directly to LRC within 30 minutes of draw; freeze at -80°C until analysis
Shipping/delivery info	NA	NA	Samples shipped to City of Hope for analysis
Storage needs	Storage available in LRC	Storage available in LRC	Storage available in LRC
Analysis center	LRC	LRC	LRC
Assay methodology	ELISA	ELISA	Real time PCR with 4070A envelope-specific primers

9.1 Sample Collection Guidelines

Additional blood samples as specified above will be drawn at the time of standard of care blood draws by the phlebotomist and transported directly to the LRC within 30 minutes of draw.

9.2 Sample Processing, Storage, and Shipment

Cytokine profile and immune response samples will be processed and stored in Lurie Research Center Neurosurgery Lab, 3-250, [name]. Samples will be assayed on site and not transported outside Northwestern University. Whole blood samples for RCR testing will be processed and stored in Lurie Research Center Neurosurgery Lab, 3-250, [name]. Samples will be batch shipped to City of Hope for analysis.

9.3 Assay Methodology

Cytokine profile and immune response samples will be analyzed using enzyme-linked immunosorbent spot (ELISA). RCR samples will be analyzed using real time PCR with 4070A envelope-specific primers.

9.4 Specimen Banking

Tumor tissue (tissue block obtained at surgery flash frozen) and cerebrospinal fluid (3ml), if obtained at the time of surgery, will be banked in the Nervous System Tumor Bank at Northwestern for future analysis.

10.0 STATISTICAL CONSIDERATIONS

10.1 Study Design/Study Endpoints

Please refer to section 2.0 and 6.0.

10.2 Sample Size and Accrual

This phase 1 study is not powered to detect statistically significant differences in efficacy. The primary endpoint of this Phase I dose-escalation study is the MTD of NSC-CRAd-S-pk7 when administered with standard radiation and chemotherapy in patients with malignant glioma. The 3+3 design has a 71% chance (49%, 17%) of dose escalating when the true toxicity rate for that dose is 20% (30%, 50%).

If all three dose levels are administered, the minimum number of patients enrolled will be 9 per arm and the maximum number of patients will be 18 per arm, for total accrual of 18-36 patients enrolled. Based upon the dose escalation schema described, groups of three to six patients will be entered at a dose level in each arm. Using this algorithm, the probabilities of dose escalation for various true DLT rates are given in Table 10. For example, if the true DLT is 50% at a dose level, there is a 17% chance that the dose would be escalated. The maximum tolerated dose determined in this study will be the recommended dose for a Phase II study. In the event the final pathology reading reveals anything other than a malignant glioma, such a patient will not be counted as one of the minimum number required without DLT for advancement to the next dose level but will be counted if a DLT is experienced.

Table 10– Probabilities of Dose Escalation	
20%	71%
30%	49%
40%	31%
50%	17%
60%	8%

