3.0 PATIENT ELIGIBILITY

The target population for this study is patients with newly diagnosed malignant glioma. This will be a single-center trial conducted at Northwestern Memorial Hospital and Northwestern Medicine Neurological Surgery clinic of Northwestern University.

Up to 36 subjects will be included in this trial. Approximately 6 potentially eligible patients are seen per month, and it is anticipated that at least 1 per month will be accrued. Potential patients are under the direct care of the Principal Investigator (PI) at Northwestern University, [name] at [contact].

Eligibility will be evaluated by the study team according to the following criteria. Eligibility waivers are not permitted. Subjects must meet all of the inclusion and none of the exclusion criteria to be registered to the study. Study treatment may not begin until a subject is registered. Please refer to Section 11 for complete instructions regarding registration procedures.

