4.2 Phase I Dose Escalation Scheme

Dose escalation will be performed independently for each arm and three to six patients will be enrolled per dose in each arm. A standard “3+3” dose escalation design will be utilized. Accrual will be staggered by two weeks between the first and second patients in a dose level. If one of three patients suffers a dose limiting toxicity (DLT), then accrual of the next three patients will also be staggered by two weeks each. However, staggering will not be required for accrual of additional patients to define the MTD at the next lowest dose level or at level 3 if no DLT is experienced in first three patients. **Table 1** below presents a summary of the dose escalation schema.

Table 1 – Dose Escalation Schema			
Cohort	Number NSCs Injected	Total Viral Dose (vp/patient)	Number of Subjects
1	50 million (5 x 10 ⁷)	6.25 x 10 ¹⁰	3-6
2	100 million (1 x 10 ⁸)	1.25 x 10 ¹¹	3-6
3	150 million (1.5 x 10 ⁸)	1.875 x 10 ¹¹	3-6

Three dose levels as described above will be tested. The two arms will be dose-escalated independently. Once the MTD is determined or after six subjects are evaluated and found to tolerate dose level 3 (the highest dose), the Phase I study will end and the results will be reviewed. The appropriate dose for a future Phase II study will be the highest administered or maximum tolerated dose from the Phase I study. Dose escalation decision rules are found in **Table 2** below.

Table 2 – Dose Escalation and Stopping Rules	
Number of Patients with DLT At a Given Dose Level	Escalation Decision Rule
0 out of 3	Enter 3 patients at the next dose level
≥ 2	Dose escalation will be stopped. Three additional patients may be entered, after discussion with the sponsor, at the next lowest dose level if only three patients were treated previously at that dose.

1 out of 3	Enter three more patients at this dose level. If none of these three additional patients experience a DLT, then dose escalation occurs, unless this is the highest dose, in which case dose escalation is stopped and the highest dose is declared the MTD. If 1 or more of these additional 3 patients have a DLT, then three additional patients may be entered, after discussion with the sponsor, at the next lowest dose level if only three patients were treated previously at that dose.
Highest dose level without \geq DLT	This will be recommended Phase II dose.

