NOTE: Whichever dose level is declared the MTD must have 6 total patients treated at that level. For example, if 3 patients are treated at level 2 and 0 patients experience DLT, escalation would then proceed to level 3. However, if \geq 2 patients at level 3 experience DLT, enrollment to level 2 would need to be re-opened to enroll an additional 3 patients at that level (with 0 or 1 DLT observed in 6 total patients) in order to declare level 2 the MTD.

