4.5 Planned Duration of Therapy

Based on projections from current clinical practice, it is anticipated that the accrual will take 12-18 months to complete.

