10.3.2 Description of Statistical Methods

10.3.2.1 General Approach

All study data will be presented in by-subject data listings. Statistical analysis will be descriptive only, with no hypothesis testing. All the endpoint data will be collected and described in summary tables for both two arms at each dose. In general, descriptive statistics (n, mean, standard deviation, median, minimum, and maximum) will be presented for continuous variables. Frequencies and percentages will be calculated for categorical and ordinal variables at each category. Statistical analyses will be performed using SAS9.4 (SAS Institute Inc., Cary, NC)

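### The stated minimum of 9 patients per arm (18 in total) is inconsistent with requiring six patients at the declared MTD; an arm that reaches level 3 and declares an MTD needs 12, or 11 with early closure of level 3

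*Combined protocol and SAP*

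**What the plan says.** **Sample size.** Section 10.2, repeated in the Study Summary, conditions on all three levels being given and then states "the minimum number of patients enrolled will be 9 per arm and the maximum number of patients will be 18 per arm". Section 10.2 adds "for total accrual of 18-36 patients enrolled".

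**Design.** Section 4.2 describes a 3+3 scheme run independently in each arm, with three to six patients per level: "Three dose levels as described above will be tested". The study ends once the MTD is determined or "after six subjects are evaluated and found to tolerate dose level 3". The NOTE after Table 2 adds: "Whichever dose level is declared the MTD must have 6 total patients treated at that level". Its worked example says that level 2 would have to be re-opened for three more patients if level 3 proves too toxic.

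**Table 2.** The row for no DLT in three patients sends the next cohort up a level and says nothing specific to level 3. The rows for excess toxicity make the extra three patients at the lower level permissive, after discussion with the sponsor.

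**Accrual.** Section 3.0: "Approximately 6 potentially eligible patients are seen per month, and it is anticipated that at least 1 per month will be accrued". Section 4.5 and the Study Summary: "it is anticipated that the accrual will take 12-18 months to complete".

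**The concern.** The lower bound counts three patients at each of three levels. The rule that defines a declarable MTD needs six at one of them. Both statements cannot describe the same completed arm.

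Section 10.2 names the MTD as the primary endpoint and as the recommended Phase II dose. An arm planned and closed at nine would have three patients at its top dose, would not meet the protocol's own condition for declaring an MTD, and would not meet the end-of-study rule. The lower figure also understates what a completed three-level trial requires when product supply, budget and calendar are planned, and the 12-18 month accrual period appears to lean on it.

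**Working it through.** There is no power calculation to reproduce: "Statistical analysis will be descriptive only, with no hypothesis testing". The check is a count of 3+3 paths, followed by a division for accrual.

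**1. The plan's own figures.** Three levels, 3-6 patients per level, two arms (Section 4.2, Table 1):
- Minimum per arm: 3 × 3 = 9. Maximum per arm: 3 × 6 = 18.
- Two arms: 2 × 9 = 18 and 2 × 18 = 36.

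These match Section 10.2 exactly, but only when the six-patient requirement is left out.

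Table 10 also reproduces. The probability of escalating at true DLT rate p is (1−p)³ + 3p(1−p)² × (1−p)³. For p = 20%, 30%, 40%, 50% and 60% it gives 70.9%, 49.4%, 30.9%, 17.2% and 8.2%, against the printed 71%, 49%, 31%, 17% and 8%. The escalation arithmetic is sound; the problem is confined to the count.

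**2. Applying the six-patient requirement.** Take arms that reach level 3, and keep levels 1 and 2 as small as possible on the way up (0 DLTs in 3 at each):

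| What happens at level 3 | Level 1 + 2 + 3 | Total | MTD |
|---|---|---|---|
| 0 of 3, expanded to six, at most one DLT in six | 3+3+6 | 12 | level 3 |
| 1 of 3, then 0 of the next 3 | 3+3+6 | 12 | level 3 |
| At least 2 of 3; level 2 re-opened to six, at most one DLT in six | 3+6+3 | 12 | level 2 |
| DLTs in the first two patients and level 3 closed there; level 2 re-opened to six | 3+6+2 | 11 | level 2 |
| Stops after 3 at level 3, no expansion anywhere | 3+3+3 | 9 | none declared |

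A full enumeration of paths reaching level 3 gives the same result. The smallest that ends with an MTD is 12 with full cohorts, or 11 if level 3 may close after two DLTs in two patients. The largest remains 6+6+6 = 18.

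**3. Totals when both arms reach level 3 and declare an MTD.**
- Full cohorts: 2 × 12 = 24 to 2 × 18 = 36.
- Early closure of level 3 in both arms: 2 × 11 = 22.
- Against the stated minimum: 12 − 9 = 3 more per arm and 24 − 18 = 6 more in total, or 3/9 = 33% above the stated figure. With early closure, 2 more per arm and 4 more in total.

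**4. Accrual.** Months = N / rate; required rate = N / months.
- At exactly 1 per month, the bottom of the Section 3.0 statement, 18 patients take 18 months: the upper end of the stated period.
- To finish within 18 months: 24/18 = 1.33 per month; 36/18 = 2.0 per month. As a share of the 6 potentially eligible patients seen monthly: 1.33/6 = 22% and 2.0/6 = 33%.
- To finish within 12 months: 24/12 = 2.0 and 36/12 = 3.0 per month, or 33% and 50% of those seen.

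**5. Does DLT observation time alone rule out 12-18 months?** Assume unlimited accrual, arms in parallel, and a DLT window after injection of 10-14 days plus about 42 days of radiation, so 52-56 days. Shortest path, with one 14-day stagger per cohort: (3 × (14+52) + 52)/30.44 = 8.2 months. With 28 days of stagger per cohort and a 56-day window: (3 × (28+56) + 56)/30.44 = 10.1 months. Longest path, six per level: 3 × 2 × (28+52)/30.44 = 15.8 months, or 3 × 2 × (28+56)/30.44 = 16.6 months. Observation time therefore does not contradict the stated period.

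**The case against.** **A reader might infer that nine per arm can never occur.** The documents do not go that far. Section 10.2 conditions only on all three levels being administered, not on an MTD being declared. Table 2 makes the lower-level expansion permissive, and Section 10.3.2.2 allows the trial to be stopped for review on separate triggers. An arm can therefore end at 3+3+3. What stands is that such an arm has no MTD under the NOTE.

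**A reader might infer that the accrual period contradicts the accrual rate.** It does not. Section 3.0 gives a floor, not a rate of one per month. The rates needed are above that floor and well inside the pool of about six seen monthly. Restating the duration flatly as 24-36 months would insert a projection that the sponsor never made. What remains is that no stated rate supports 12-18 months for 24-36 patients.

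**A reader might infer that no DLT in three patients at level 3 is left unspecified.** Section 4.2 covers it outside the table. The end-of-study sentence requires six subjects at level 3, and the staggering sentence provides for further patients there when the first three have no DLT. Only the table row is incomplete.

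**A reader might also want a figure above 36**, because untreated patients are replaced (Section 4.1) and final-pathology exclusions without a DLT do not count toward escalation (Section 4.3). The documents give no loss rate, so no number can be attached.

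Finally, it is fair to say that the nine is a projection, not a stopping rule. Conduct follows Section 4.2, no analysis uses the figure, and the ceiling of 36 is untouched. That limits the consequences but does not make the stated minimum correct.

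**Conclusion.** The point holds in conditional form. For an arm that reaches level 3 and declares an MTD, the minimum is 12 with full cohorts, or 11 if level 3 closes after DLTs in its first two patients; the plan states 9. If both arms do so, the range is 24-36 with full cohorts (low end 22 with early closure in both), not 18-36. The maximum is correct.

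This rests on taking the NOTE and the end-of-study rule as they stand. It is not a floor for the whole trial: the arms escalate independently, and an arm that stops at level 1 or 2 lies outside the condition and may be smaller.

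The accrual point is secondary. The 12-18 months agrees with the stated floor only through the 18-patient total; for 24-36 patients it needs a higher rate that the plan does not state.

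**What to change.** 1. In the Study Summary and Section 10.2, restate the range, for example: *If all three levels are administered and an MTD is declared, 12-18 evaluable patients per arm (24-36 in total); 11 in an arm where level 3 closes after DLTs in its first two patients.* Say that replacements for untreated patients and final-pathology exclusions come on top, and how this sits with the cap of 36 subjects in Section 3.0.
2. Reconcile Table 2 with the text of Section 4.2 and the NOTE in two places: the row for no DLT in three patients as it applies at level 3, and the permissive wording on lower-level expansion against the six-patient requirement. The sponsor must decide how these are resolved. If a smaller arm is meant to remain possible, say that it ends without a declared MTD.
3. In Section 4.5 and the Study Summary, either state the expected accrual rate behind the period (about 1.3-2.0 per month to finish 24-36 patients within 18 months) or lengthen the period, and align Section 3.0 with it.

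The cost is wording only. The stated minimum, and possibly the duration, become less favourable; the maximum of 36 evaluable patients and Table 10 are unchanged.
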